Risk/Benefit Assessment

- Include a thorough description of how risks and discomforts will be minimized (per 45 CFR 46.111(a) (1 and 2)). Consider physical, psychological, legal, economic and social risks as applicable. If vulnerable populations are to be included (such as children, pregnant individuals, imprisoned persons or cognitively impaired adults), what special precautions will be used to minimize risks to these subjects? Also identify what available alternatives the person has if he/she chooses not to participate in the study. Describe the possible benefits to the subject. What is the importance of the knowledge expected to result from the research?

Potential Risks. No adverse events are anticipated. Participation in all portions of the study is voluntary and participants can withdraw at any time. The risks associated with all portions of this study are minimal and rare. Participation in focus groups or a psychosocial symptom management intervention are associated with few negative side effects. The focus groups, intervention sessions, and assessments will cover topics including physical health (e.g., cancer diagnosis and treatments), physical symptoms (e.g., pain, fatigue), psychological distress, symptom interference, self-efficacy for symptom management, personal values, and experiential avoidance, all of which may request participants to provide sensitive and personal information. Participants may feel embarrassed or uncomfortable with disclosing this information. There is also the possibility of breach of confidentiality. For example, in a group setting, such as a focus group, there is risk of disclosure of personal information by another participant. Additionally, there is some risk of loss of confidentiality inherent to the use of videoconferencing to conduct the study intervention sessions. All efforts will be made to remain sensitive to participant's needs, HIPAA requirements, and confidentiality procedures (see below). To ensure that there are no changes in potential risk during the course of the study and that confidentiality is maintained, the study team will implement a Data and Safety Monitoring Plan.

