Pregnant women will not be excluded from this study; thus, it is possible that an AYA patient or their caregiver participating in this study may be pregnant as the majority of female participants will be of childbearing age. The risk to pregnant women of participating in a focus group or psychosocial symptom management intervention is extremely low. No study activities will directly impact the health of the pregnant woman or her fetus. Pregnant women providing consent/assent will be fully informed regarding the minimal foreseeable impact of the research on the fetus. The primary risks of participation in the proposed study are the potential for increased distress and loss of confidentiality, and significant steps will be taken to minimize these risks (see above). [name] (Co-I) is a pediatric oncologist. He will review the chart of any pregnant participant, consult with the participants' OB/GYN as necessary to confirm the appropriateness of her participation in the proposed study, and ensure that there are no contraindications for participation in all parts of this study. The anticipated benefits to the overall wellbeing of the participant (see below) and minimal risk to the woman and her fetus are reasonable to warrant participation in the proposed study.

Use of Zoom during Focus Groups:

To ensure security while using Zoom, the following recommended steps will be taken:

Prior to Meetings:

Generate meeting ID automatically – Unique meeting IDs expire 30 days after the meeting has occurred, and provide protection if a meeting ID was shared accidentally to a public audience.

Require meeting password – Don't share your meeting password.

Enable waiting room – Review attendees before admitting them to the meeting.

During Meetings:

Lock meeting – Prevents any additional participants from joining.

Screen sharing is host only – By default, only hosts can share their screens. Hosts can grant individuals the ability to share in the participant panel.

Remove unwanted participants - Beside the participants name (in the Participant pane) select More, and then select Remove.

Report participant - If a user made attempts to disrupt your meeting either by speaking, chatting, or showing offensive video, select the option Report which is available under the Security icon or on each participant's name. This will alert Zoom Support.

Recording Meetings:

Attendees will be advised that they are being recorded.

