
The proposed study carries minimal risk. Data obtained from participants will include information from medical chart review, patient and caregiver interviews, and self-report inventories. The PI, Co-Is, and key personnel consider the management of participant information and data as a key priority. Best practices for confidentiality and data management will be observed.

All participants will continue their usual medical care over the course of their participation in the study and be informed that choosing to participate in the study will in no way impact the treatment they receive at Duke University Medical Center (DUMC). All patient participants will continue to be monitored by their physicians at the Duke Cancer Institute (DCI) and Duke Children's Hospital and Health Center (Duke Children's) throughout the course of the study; thus patients' doctors will provide monitoring of their overall medical status. If a health concern is identified during contact with study staff, the patient's treating oncologist will be contacted, and appropriate referrals for medical treatment will be provided to patients. All research personnel who have direct contact with patients will be trained to observe and report any adverse events. The PI will report any adverse event to Duke's Institutional Review Board (IRB) in real time. An adverse event is defined as any untoward medical event occurring during the clinical evaluation, which is causally related to the study protocol. A serious adverse event is defined as any event which results in death, is immediately life threatening, results in persistent or significant disability/incapacity, results in patient hospitalization, or is serious for any other reason representing significant hazard. We will appoint two data safety officers. One data safety officer will be a physician who is not associated with this study. The appointed physician officer will have experience with clinical research and trials and have a thorough understanding of adverse events. The other data safety officer will be a senior investigator who has expertise in psychosocial symptom management and will have an annual responsibility to evaluate our current methods of assessment and intervention and identify any problems. All adverse events will be reported to Duke's IRB and the data safety officers in real time.

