The sponsor-investigator or principal investigator (PI), and Duke Cancer Institute (DCI), through the PRMS and PRMC, will monitor this clinical research study. For internal review, the sponsor-investigator or PI will continuously monitor and tabulate adverse events. The study team will make reports to the Duke University Hospital System (DUHS) Institutional Review Board (IRB). If an unexpected frequency of Grade III or IV events occur, depending on their nature, action appropriate to the nature and frequency of these adverse events (AE) will be taken. This may require a protocol amendment, dose de-escalation, or potentially study closure. The study sponsor-investigator or PI will also continuously monitor study conduct, data, and safety to ensure:

- Interim analyses occur as scheduled.
- Stopping rules for toxicity and/or response are met.
- Risk/benefit ratio is not altered to subject detriment.
- Appropriate internal AE and outcomes monitoring is performed.
- Over-accrual does not occur.
- Under-accrual is addressed with appropriate amendments or actions.
- Data are being appropriately collected in a reasonably timely manner.

PRMS protocol review begins with the PRMC. PRMC new protocol reviews focus on scientific relevance, study design, biostatistical input adequacy, protocol prioritization, feasibility of study completion within a reasonable time frame and trial risk assessment. The sponsor-investigator or PI will abide by PRMC risk level assessment. PRMC also conducts annual scientific progress reviews on protocols open to enrollment and focuses on protocol prioritization, accrual, and scientific progress. The PRMC conducts reviews at the time of IRB annual renewals and maintains documentation in eIRB/iRIS.

During the initial PRMC approval, the PRMC determines the monitoring risk level and frequency which will be commensurate with the type and level of intervention, phase, endpoints, degree of risk, size, and

protocol complexity. The DCI monitoring team will conduct formal, independent monitoring according to the risk level and the PRMC monitoring plan until the study is closed to enrollment or subjects are no longer receiving study drug or other interventions that are more than minimal risk.

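### The adverse event definition requires a medical event caused by the study, which drops unrelated non-serious events and leaves distress, confidentiality breaches and serious events unclear

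*Combined protocol and SAP*

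**What the plan says.** Data & Safety Monitoring defines an adverse event as "any untoward medical event occurring during the clinical evaluation, which is causally related to the study protocol". The next definition is built differently: "A serious adverse event is defined as any event which results in death", followed by the other usual seriousness criteria and a catch-all for significant hazard, with no condition on cause. Adverse events go to the IRB and two data safety officers in real time, and Protection Against Risk repeats the IRB duty. For internal review, "the sponsor-investigator or PI will continuously monitor and tabulate adverse events". Action follows "If an unexpected frequency of Grade III or IV events occur"; no grading scale or threshold is given, and that sentence goes on to call these events adverse events.

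Under Potential Risks the plan states: "No adverse events are anticipated". Under Vulnerable Subjects, in the paragraph on pregnancy but worded for the study as a whole, it states: "The primary risks of participation in the proposed study are the potential for increased distress and loss of confidentiality".

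Distress is handled by consultation, reporting to the PI, referral and removal from the trial (Protection Against Risk; Data & Safety Monitoring). None of these is said to be logged as an adverse event. The Aim 2 analysis in Data Analysis & Statistical Considerations covers feasibility, acceptability, outcomes and intervention targets, and has no safety tabulation.

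**The concern.** Harm can be compared between arms only if events are recorded before anyone decides what caused them. Here causation is part of the definition, so the judgement comes first and unrelated events leave no trace in the count.

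Those placed to judge know the allocation. The coordinator randomizes participants (Aim 2: Pilot RCT) and also monitors their psychological status for the PI, who supervises the therapist weekly (Protection Against Risk). In advanced or recurrent cancer, worsening distress is easily put down to the disease. Control participants receive a booklet and usual care, so little in that arm could be judged study-related. Counts of related events alone would therefore not be comparable between arms.

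The pilot is meant to inform a larger trial, and a promising result may lead to rapid local dissemination (Innovation, item 3). Under this definition, a report of few or no adverse events would say little about harm.

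**Working it through.** The plan states no event rate, safety sample size or stopping figure, so there is nothing of its own to reproduce. The check is a reading of the definitions, followed by a calculation for scale.

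**Step 1. Apply the definitions to the events that matter.**

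| Event | Adverse event? | Serious adverse event? | Stated to be reported or tabulated? |
|---|---|---|---|
| Non-serious medical event, judged related | Yes | No | Yes |
| Non-serious event, judged unrelated | No | No | No |
| Death or hospitalisation, judged unrelated | No | Yes if the serious definition stands alone; no if a serious event must first be an adverse event | Not stated |
| Non-serious increased distress, judged related | Depends on whether *medical* includes psychological | No | Depends |
| Non-serious increased distress, judged unrelated | No | No | No |
| Confidentiality breach | Hardly *medical* | Only if judged a significant hazard | Unclear at best |

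The second and fifth rows follow directly from the text. The third, fourth and sixth are ambiguities that the text does not settle.

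**Step 2. Does outcome measurement fill the gap?** Depression and anxiety are scheduled for both arms at baseline (A1), post-treatment (A2) and follow-up (A3) (Study Measures). Aim 2 analyses change by paired t-tests, with effect sizes and confidence intervals for each arm. A paired change needs a score at both time points. A participant removed for distress may have no later score and would then drop out of the mean. A mean also does not show how many individuals worsened.

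**Step 3. Would the definition alone account for the missing comparison by arm?** No. Tabulation is described without reference to arm, and Aim 2 has no safety analysis even for related events. This is a second, separate gap.

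**Step 4. Scale.** Inputs: 24 intervention and 16 control participants (Study Design).

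If no events are seen in n participants, the upper one-sided 95% bound is 1 − 0.05^(1/n):
- n = 24: 1 − 0.05^(1/24) = 0.117, or 11.7%
- n = 16: 1 − 0.05^(1/16) = 0.171, or 17.1%

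The chance of at least one event at true rate p is 1 − (1 − p)^n. The rates are assumptions, since the plan gives none:

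| Assumed p | n = 24 | n = 16 |
|---|---|---|
| 5% | 71% | 56% |
| 10% | 92% | 81% |
| 20% | 99.5% | 97% |

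Over this range, all-cause recording would more likely than not capture at least one event in each arm. The bounds show that the comparison would still be imprecise.

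**The case against.** The strongest reply is that this is a minimal-risk pilot with several layers of protection. Serious events are defined regardless of cause. Distress scores are collected in both arms at every assessment. Staff are trained to watch for distress and report it. One safety officer has psychosocial expertise and a yearly duty to look for problems. The word *medical* is undefined, and a team of psychologists and a psychiatrist could well read it to include psychological events. With 24 and 16 participants, no comparison of harm would be precise.

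Much of this stands, and it rules out several stronger readings that a reader might infer:

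- *Every unrelated event is excluded.* Not supported: the serious event definition has no causality condition, so unrelated deaths and hospitalisations may qualify. What is missing is how the two definitions relate and what route serious events take.
- *Distress is excluded, or could never be seen.* Not supported: its status as an adverse event is ambiguous, and it is measured in both arms. What is missing is a count of events such as referrals and removals.
- *The definition is the reason nothing is counted by arm.* Not supported, as Step 3 of the working shows.
- *Staff are instructed to screen events out.* No such step is described. The effect comes from applying the definition as written, by people who know the arm.

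The reply does not rescue the non-serious unrelated events, which have no place in the record. Nor does imprecision justify filtering by attribution, which would add bias to imprecision.

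A practical objection also stands. Deleting the causality clause alone would extend real-time IRB reporting to every cancer symptom, and the intervention arm's four extra contacts could raise its counts through closer observation. The fix has to deal with both.

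**Conclusion.** The point holds in limited form and is worth correcting. As written, non-serious events judged unrelated are outside the safety count, and the plan leaves open whether its two named primary risks are counted. It also leaves open how serious events relate to adverse events and how they are reported and tabulated. The absence of any safety count by arm is a separate omission.

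The number of events affected cannot be computed from the documents. The conclusion rests on reading the definition literally and on the inference that the coordinator and PI know the allocation; no blinding of them is described. It does not depend on the assumed event rates. Clinical handling of distress is not in question.

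**What to change.** 1. Take causality out of the adverse event definition and record relatedness as a separate field.
2. State that psychological events and confidentiality breaches are included.
3. State that serious events are recorded regardless of cause, how they relate to adverse events, and how they are reported and tabulated.
4. At minimum, log deaths, hospitalisations, distress-related referrals or removals, and confidentiality breaches in both arms regardless of cause. Use the same enquiry at A2 and A3 in both arms, so that the four extra intervention contacts do not drive the counts. Use chart review and study records for participants who miss those assessments.
5. Add to Aim 2 a table by arm with denominators 24 and 16.
6. Reword the reporting sentences in both Protection Against Risk and Data & Safety Monitoring so that real-time IRB reporting stays limited to related events.

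The cost is a few sentences, a short log and a few enquiry items for 40 participants. Chart review and distress monitoring are already planned, so the extra recording is modest. The counts will remain imprecise and should be reported descriptively. Clinical handling of distress is unchanged.
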